8.5.2 Safety Monitoring Rules for Platelet Count Results

If a subject's absolute platelet count is $100,000/\text{mm}^3$ or less, then the subject's platelet counts should be monitored weekly. In the event of a platelet count $< 75,000/\text{mm}^3$, additional laboratory investigations may be conducted ([Table 4](#)). The frequency of monitoring and additional lab tests will be determined by the Investigator in consultation with the Sponsor Medical Monitor (or designee).

Table 4 Additional Labs to be Performed in the Event of a Platelet Count < 75,000/mm³

To Be Performed at Local Lab
Peripheral smear (should be performed locally, fixed and sent to central lab for review)
Fibrinogen split products or D-dimer on fresh blood
To Be Performed at Central Lab
Citrated sample for platelets
Coagulation panel (PT/INR, aPTT)
CBC with reticulocytes and mean platelet volume (MPV)
Fibrinogen
von Willebrand factor
Total globulins, total IgA, IgG and IgM
Complement: total C3, total C4, Bb, C5a
hsCRP
Serology for:
HBV, HCV, HIV (if not done for screening)
Rubella
CMV
EBV
Parvo 819
Helicobacter pylori
Auto-antibody screen:
Antiphospholipid
Rheumatoid factor
Anti-dsDNA
Anti-thyroid
To Be Performed at Specialty Lab(s)
Antiplatelet antibodies and Anti-PF4 assay
Anti-ASO antibody

Note: The following labs may change as additional data is assessed, and sites will be updated regarding any changes.

8.5.3 Safety Monitoring for Bleeding Events

Subjects will be evaluated for occurrence of bleeding events continuously after the start of Study Drug treatment (Day 1) up to Day 260 for all cohorts. All bleeding events are considered AEs and reported on adverse event case report form.

Bleeding events that are either major or CRNMB (as defined below) will need to be monitored and treated immediately. Subjects with a suspected bleeding event will undergo additional testing if deemed appropriate by the treating physician and an (S)AE case report form will be completed. In addition, if bleeding is considered significant, Hb, HCT, aPTT, PT, INR, FXI activity and antigen, and platelet count are to be obtained. In addition, approximately 2 mL of

K2EDTA anticoagulated blood will be collected and resulting plasma must be stored allowing for a centralized assessment of ISIS 416858 concentrations.

In addition, if a minor bleeding event occurs, the Investigator should notify the Sponsor Medical Monitor (or designee) and additional testing of coagulation parameters (aPTT, PT, INR), platelet count, and platelet volume may be performed.

Definitions:

Major bleeding (MB) is defined as one of the following:

1. Fatal bleeding
2. Symptomatic bleeding in a critical area or organ, such as intracranial, intraspinal, intraocular, retroperitoneal, intraarticular if in a major joint, or pericardial, or intramuscular with compartment syndrome
3. Clinically overt bleeding leading to transfusion of 2 units of packed red blood cells or whole blood or a fall in Hb of 20 g/L (1.24 mmol/L) or more within 24 hours

Clinically-Relevant Non-Major Bleeding (CRNMB) is defined as overt bleeding not meeting the criteria for MB but that resulted, for example, in medical examination, intervention, or had clinical consequences for a subject (Biller et al. 2007).

Minor bleeding events are those that do not fulfill the criteria for MB or CRNMB events (defined above), for example excess bruising, petechiae, gingival bleeding on brushing teeth.

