2 ANALYTICAL PLAN

2.1 General Overview of Analyses

2.1.1 General Statistical Methods

Descriptive summary statistics including number of patients, mean, standard deviation, median, and range (minimum, maximum) for continuous variables, and counts and percentages for categorical variables will be used to summarize most data. All statistical tests will be conducted using 2-sided tests with 5% Type I error rate unless otherwise stated.

PK parameters will be summarized using number of patients, mean, standard deviation, coefficient of variation (CV), geometric mean, median, minimum, and maximum.

All analyses and tabulations will be performed using SAS® Version 9.2 or higher and Phoenix/WinNonlin version 6.1 or higher on a PC platform.

A separate analysis for on-treatment period might be provided if deemed necessary.

Pooled groups:

Patients who are placebo-treated will be pooled and analyzed as a single placebo group.

Patients who are ISIS 416858-treated may be pooled and summarized as the ISIS 416858 total group.

Baseline definition:

Unless otherwise specified, baseline for all safety laboratory results will be defined as the last non-missing measurement prior to the first dose. For post-dialysis Blood Urea Nitrogen (BUN) measures for Urea Reduction Ratio (URR) determination, post-dialysis baseline will be defined as the last non-missing post-dialysis measurement prior to the first dose

Analytical visits:

All post-baseline data will be summarized according to the visit windows in the table below. For patients who have multiple visits within a window, the average will be used in the summary for continuous variable and the worst case result will be used for categorical variable.

Table I Visit window for Clotting

Analysis visit	Visit window
Screening	<1
Baseline	last non-missing measurement prior to the first dose
Day8	[2, 11]
Day 15	[12, 21]
Day29	(22, 35]
Day43	[36, 49]
Day 57	[50, 63]
Day71	[64, 77]
Day 85	[78, 91]
Day99	(92, 105]

Day 113	[106, 116)
Day 120	[117, 126)
Day 134	(127, 140)
Day 148	(141, 154)
Day 162	[155, 168)
Day 176	[169, 182]
Day 190	(183, 196]
Day 204	[197, 210]
Day 218	[211, 224]
Day 232	[225, 238]
Day 246	(239, 252]
Day 260	[253, 266]

Table 2 Visit window for Vital Signs

Analysis visit	Visit window
Baseline	last non-missing measurement prior to the first dose
Day 5	(2, 6)
Day 8	[7, 9]
Day 12	[10, 13]
Day 15	[14, 17]
Day 22	[18, 25)
Day 29	[26, 32)
Day 36	[33, 39)
Day 43	[40, 46]
Day 50	[47, 53]
Day 57	[54, 60]

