2.4 Pharmacodynamic Analyses

The pharmacodynamic analysis will be conducted on the Per Protocol Population and will be presented according to treatment group and ISIS 416858 total. The baseline is defined as the latest- assessment prior to first dose of study drug.

Change and percent change from baseline FXI activity and antigen levels and aPTT will be summarized by treatment and visit separately. Individual results will be presented in data listings by treatment. Figures of the mean FXI activity and antigen levels and aPTT results as well as change and percent change from baseline will be provided by treatment group, and scheduled visit.

Change and percent change from baseline in FXI activity and antigen levels and aPTT will be compared between each of the ISJS-416858 treated group and pooled placebo group using the ANOVA or Wilcoxon Rank Sum test, as appropriate. The normality will be tested by applying Kolmogorov-Smirnov test on the residuals (difference between individual values and group mean). Numeric values will be rounded to 5 decimal places when applying Wilcoxon Rank Sum test or Kolmogorov-Smirnov test.

Frequency and percent of patients with average FXI activity .1, -2, s>.3, ..., :9.0U/mL during Day 50 to Day 176 (inclusive) up to last dose+ 7 days will also be provided.

The incidence and events for any aPTT>160s will be summarized by treatment and visit.

The clotting assessment will be conducted on the Per Protocol Population and will be presented according to treatment group and ISIS 416858 total.

The clotting assessment will consist of a quantitative scale by descriptive category (see details in table 1) and will be performed by trained personnel.

Table 1 Clotting Scale

Inspection site	Category 1	Category 2	Category 3	Category4
Air Trap	No clotting	Fibrinous ring with no clot formation on venous chamber filter	Clot formation on venous chamber	Coagulated system (treatment cannot continue without new setup)
Dialyzer	Clean dialyzer	Blood stripes affecting less than 5% of the fibers seen at the surface of the dialyzer	Blood stripes affecting 5% or more of the fibers seen at the surface of the dialyzer	Coagulated filter

Overall score is the highest of the individual component scores

Individual Category Summary

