Patient percentage of events greater or equal to 3 will be summarized for 2 periods (before Week 8, after Week 8 and up to last dose+ 7 days). The change of the percentages will be summarized and analyzed by ANOVA.

Most severe clotting category

In order to examine the correlation of FXI activity level and clotting, a separate summary on the most severe clotting category will be provided for patients with average Pre-dialysis FXI activity :::{.1}, :::{.2}, :::{.3}, ... , :::{1.0} U/mL during Week 8 and Week 26 (Day 176) (inclusive) for ISIS 416858 treated patients only.

Additional summary for frequency and percent of events with ≥ 3 clotting category with average Pre-dialysis FXI activity :::{0.1}, :::{.2}, :::{.3}, ... , :::{1.0} U/mL during Week 8 and Week 26 (Day 176) (inclusive) will also be provided.

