6.2.2 Safety

Subjects with a suspected bleeding event will undergo additional testing if deemed appropriate by the treating physician and an (S)AE case report form will be completed. In addition, if

bleeding is considered significant, hemoglobin (Hb), hematocrit (Hct), aPTT, PT, INR, and platelet count are to be obtained, and approximately 2 mL of K2EDTA anticoagulated blood will be collected. The resulting plasma must be stored allowing for a centralized assessment of ISIS 416858 concentrations.

If the platelet value or liver enzyme tests are uninterpretable (e.g., due to clumping, hemolysis or quantity not sufficient) or missing, a repeat blood specimen must be re-drawn as soon as possible (ideally within 7 days).

Subjects that withdraw from the study due to a change in dialysis modality or to undergo renal transplantation should notify the Sponsor Medical Monitor (or designee) and conduct the early termination procedures identified in [Appendices A](#) and [C](#) prior to the change or the surgery as appropriate. Whenever possible, a coagulation panel and PK blood sample should be collected prior to the initiation of renal transplant surgery. Additionally, at approximately 48 hours post-transplant, additional blood samples should be collected for Coagulation Panel ([Appendix B](#)) and ISIS 416858 plasma concentration (Appendix C). Any clinically-significant bleeding such as CRNMB and MB should be recorded and reported to the Sponsor Medical Monitor (or designee).

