8.6.3 Stopping Rule for Bleeding

If an event of Major Bleeding or CRNMB event occurs, the Investigator must notify the Sponsor Medical Monitor (or designee) and the subject should be closely monitored (vital signs, lab tests such as Hb, HCT and platelet count, additional outpatient visits, overnight stays and coagulation tests may be needed) throughout the treatment and during the post-treatment evaluation period.

In the event of Major Bleeding or CRNMB (see definitions in [Section 8.5.3](#)) as assessed by the Investigator, dosing of a subject with Study Drng (ISIS 416858 or placebo) may be stopped permanently. The follow-up schedule for any events meeting this discontinuation criterion will be determined, including the suitability of the subject for resumption of dosing by the Investigator in consultation with the Sponsor Medical Monitor (or designee).

Treatment Precautions:

Recommendations to manage bleeding in a patient will be provided to all study sites:

Specifically, if a patient has Major Bleeding or Clinically Relevant Non-Major Bleeding during the trial, the following measures are to be considered by the Investigators to control that bleeding:

1. Delay of the next injection or discontinuation of treatment in consultation with Sponsor Medical Monitor (or designee) per [Section 8.6.3](#).
2. Review and discontinue concomitant medications that could exacerbate bleeding.
3. Mechanical compression/ Surgical intervention/haemostasis.
4. General volume management: fluid replacement & hemodynamic support.
5. Transfusion (whole blood/packed cells/FFP/platelets).

If bleeding cannot be controlled by these measures, consider administration of one of the following procoagulants (according to the dosages advised in the package insert), FXI concentrate (Hemoleven®), Recombinant Factor Vila (NovoSeven®), or 4-factor concentrate (prothrombin complex concentrate).

ISIS 416858 treatment does not directly inhibit circulating FXI, only production of this clotting factor in the liver. Therefore, the dose of fresh frozen plasma (FFP) or factor concentrate given should aim to increase FXI activity above 0.3 U/mL and should recognize that the half-life of circulating FXI is approximately 50 hours when considering the potential need for re-administration. Additionally, the time necessary to obtain a FXI concentration locally and to infuse FFP should be taken into consideration.

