Appendix A Schedule of Procedures *Continued*

Notes: -If not specifically labeled, "X" means Pre-dialysis. Please refer to [Appendix C](#) for PK blood sampling procedures. A 10-minute time window applies to all procedures to allow for flexibility where multiple procedures are scheduled at the same time-Subjects who terminate the study early should complete the procedures indicated for the early term visit (Treatment or Post-Treatment Evaluation Period). For subjects that undergo renal transplant, please refer to [Section 6.2.2](#).

* Only applies to PK subgroup participants

- 1 Women!, 55 years who are not surgically sterile and have 12 months of spontaneous amenorrhea as confirmation of menopause
- 2 For all women, to be done once at S-28 to S-14. For women of child bearing potential who are not surgically sterile, a serum test at all time points after Day 1
- 3 BP, HR, RR, temp
- 4 BP at selected visits will be assessed 3 times, approximately 5 minutes apart
- 5 If the platelet value or liver enzyme tests are uninterpretable (e.g., due to clumping, hemolysis or quantity not sufficient) or missing a repeat blood specimen should be re-drawn as soon as possible (ideally within 7 days) and reviewed prior to dosing. Valid platelet counts must be conducted every 2 weeks and reviewed prior to dosing
- 6 The rate/frequency of clotting on the dialysis filters and circuit will be measured as an exploratory PD analysis
- 7 At screening Study Day S-14 (± 3) and S-7 (± 3), subjects should receive 2 noncontiguous SC injections of 0.75 ml saline. This injection will follow the same procedures as injections of the Study Drug (ISIS 416858 or placebo) during the treatment period. Specifically, during the screening period on Study Days S-14 (± 3) and S-7 (± 3), subjects should receive 2 noncontiguous SC injections of 0.75 ml saline immediately after dialysis when blood is returning to the subject but must be within 2 hours after dialysis (preferably within 15 minutes of the conclusion of dialysis)
- 8 Urea Reduction Ratio is a measure of serum BUN, collected before and just after dialysis, and is used to estimate the reduction in urea as a result of dialysis as a measure of efficiency of the dialysis procedure. In addition, the subject's most recent KW value, preferably single-pooled Kt/v if possible will be collected directly from the subject's chart

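### The SAP has no rule keeping unscheduled, non-pre-dialysis or post-replacement coagulation samples out of the FXI and aPTT summaries; the aPTT>160s counts and borderline FXI categories are most exposed

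*Combined protocol and SAP*

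**What the plan says.** **Scheduled samples.** The notes to protocol Appendix A state: "If not specifically labeled, 'X' means Pre-dialysis". The coagulation panel carries no other label, so its scheduled samples precede dialysis. Appendix B places aPTT, PT, INR, FXI antigen and FXI activity in that panel.

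**Unscheduled samples.** Four protocol sections can generate aPTT or FXI results outside the schedule:
- 8.5.3, for a significant bleed: "if bleeding is considered significant, Hb, HCT, aPTT, PT, INR, FXI activity and antigen, and platelet count are to be obtained". It also permits aPTT testing after a minor bleed.
- 8.6.3, which says further coagulation tests may be needed after a major or clinically relevant non-major bleed.
- 6.2.2, which asks for a coagulation panel about 48 hours after renal transplant. It also gives its own bleed work-up, without FXI: "bleeding is considered significant, hemoglobin (Hb), hematocrit (Hct), aPTT, PT, INR, and platelet count are to be obtained".
- 8.5.2 (protocol Table 4), which includes aPTT in the low-platelet work-up.

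None of them sets a time relative to a dialysis session or to replacement therapy. Section 8.9.1 allows heparin during dialysis. On replacement, 8.6.3 says "the dose of fresh frozen plasma (FFP) or factor concentrate given should aim to increase FXI activity above 0.3 U/mL" and gives a half-life of about 50 hours for circulating FXI.

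**Analysis.** SAP 2.1.1: "All post-baseline data will be summarized according to the visit windows in the table below". And: "For patients who have multiple visits within a window, the average will be used in the summary for continuous variable". SAP Table 4 gives the windows for the coagulation panel. SAP 2.4: "The incidence and events for any aPTT>160s will be summarized by treatment and visit". Only the FXI-by-clotting summaries at the end of SAP 2.4 are restricted, to "patients with average Pre-dialysis FXI activity". The FXI category table earlier in that section covers Day 50 to Day 176 and has no such restriction.

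**The concern.** A scheduled aPTT is a pre-dialysis value. One drawn during a bleed may be drawn while dialysis heparin is active. An FXI value drawn after plasma or factor concentrate reflects the replacement as well as the study drug. Following SAP 2.1.1 literally mixes these with the pre-dialysis values.

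The trigger overlaps the primary safety outcome (major plus clinically relevant non-major bleeding). If bleeding differs between arms, the number of such samples would differ too. A heparinised sample could add a subject to the aPTT>160s table for reasons unrelated to FXI lowering. A post-replacement sample would make FXI suppression look weaker in a subject who bled.

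The SAP uses the pre-dialysis restriction for one FXI average and omits it for a nearly identical one in the same section. That suggests an oversight rather than a choice.

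**Working it through.** The plan gives no figure to reproduce here, and both documents say the sample size has no statistical rationale. The check asks whether timing alone could exclude triggered samples, then how much one such sample could matter. All aPTT and FXI values below are assumptions unless a source is given.

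**1. Do the windows exclude anything?** I read the 22 post-baseline windows of SAP Table 4 as closed intervals, because the brackets are mixed in the extracted text. Every day from 2 to 266 then falls in exactly one window, so an unscheduled sample cannot drop out by date.

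**2. Arm size.** 204/3 = 68 per cohort. At 3:1 this gives 68 × 3/4 = 51 per active dose and 3 × 17 = 51 pooled placebo. One subject is 1/51 = 2.0%.

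**3. aPTT.** Window value = (scheduled + triggered)/2. Shift in the arm mean = (window value − scheduled)/51.

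| Scheduled (s) | Triggered (s) | Window value (s) | Mean shift (s) | Counts as >160 s? |
|---|---|---|---|---|
| 45 | 100 | 72.5 | 0.54 | no |
| 45 | 180 | 112.5 | 1.32 | yes |
| 60 | 180 | 120 | 1.18 | yes |
| 60 | 240 | 150 | 1.76 | yes |

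No window average exceeds 160 s. The count is affected because it takes any value.

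**4. FXI category.** I assume the category cut-offs are upper limits in steps of 0.1 U/mL, since the signs are lost in extraction. SAP Table 4 has 10 scheduled visits from Day 50 to Day 176 (Days 50, 64, 78, 92, 106, 120, 134, 148, 162 and 176).
- All ten at 0.20, plus one value of 0.3: (10 × 0.20 + 0.3)/11 = 0.209.
- All ten at 0.20, plus one value of 0.8: (10 × 0.20 + 0.8)/11 = 0.255.
- If window values are averaged first, which the SAP does not settle: (9 × 0.20 + 0.25)/10 = 0.205 and (9 × 0.20 + 0.50)/10 = 0.230.

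In all of these the subject leaves the 0.2 category, which is the target level in protocol 2.4. A subject further from the boundary does not move:
- Ten at 0.15 plus one at 0.5: (1.5 + 0.5)/11 = 0.182.
- Ten at 0.17 plus one at 0.35: (1.7 + 0.35)/11 = 0.186.
- With three values of 0.35: (1.7 + 1.05)/13 = 0.21, the first time this subject crosses.

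**5. FXI group mean.** For 0.20 plus one value of 0.3, the shift in one window is (0.25 − 0.20)/51 = 0.001 U/mL. For 0.20 plus 0.8, it is (0.50 − 0.20)/51 = 0.006 U/mL.

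**6. Carry-over into scheduled samples.** For an assumed rise from 0.2 to 0.5 and the stated 50-hour half-life, FXI at h hours is 0.2 + 0.3 × 0.5^(h/50). This gives 0.42 at 24 h, 0.31 at 72 h and 0.23 at 168 h. A scheduled sample soon after replacement can also be affected.

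**7. Frequency.** Protocol 2.2 cites hospitalised haemorrhage in 1 of 7 patients over 3 years. At constant hazard the 26-week risk is 1 − (6/7)^(0.5/3) = 2.5%, or 51 × 0.0254 = 1.3 subjects per arm. The definition of clinically relevant non-major bleeding is broader than hospitalisation, so an assumed range of 2% to 20% gives about 1 to 10 subjects.

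**8. Average effect on aPTT visit means.** Suppose 1 to 10 subjects per arm each give one 165 s sample against a scheduled 45 s. Each moves one window value by (45 + 165)/2 − 45 = 60 s, so 60/51 = 1.18 s in the arm mean. Spread over the 16 on-treatment windows, the expected shift is 1.18/16 = 0.07 s to 10 × 1.18/16 = 0.74 s.

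**The case against.** The strongest reply is that inclusion is inferred from silence. The SAP never says that bleed work-up results enter the PD dataset. Section 8.5.3 names no laboratory for the aPTT and FXI tests, and the averaging rule speaks of visits. Notes to file on FXI levels, an unblinded local laboratory, dialysis times and the per-protocol set are listed by title only. A reader might infer that triggered values are in fact averaged in and that the PD results partly measure heparin, replacement and bleeding frequency. The documents do not support that. They show only that no written rule prevents inclusion. The wording nevertheless leans towards it: the post-transplant sample is called a coagulation panel, as in SAP Table 4; the low-platelet aPTT goes to the central laboratory; and SAP 2.3.4 limits ALT and AST categories to central data but says nothing similar for coagulation.

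Other points stand in part:
- SAP 2.4 uses the Per Protocol population, which excludes subjects missing more than 5 doses. Someone stopped permanently after dose 20 or earlier misses at least 6. This removes some bleeders and most transplant recipients. It does not remove those whose dosing was only delayed or resumed, and protocol 10.6.4 assigns PD to the Safety population, which keeps them all.
- The FXI part of the bleed work-up rests on 8.5.3, because 6.2.2 omits FXI. No text says the sample follows replacement, and factor concentrate is considered only if other measures fail.
- The Wilcoxon alternative in SAP 2.4 limits the leverage of one outlier in the comparisons, the PD figures are by scheduled visit, and the FXI category table stops at last dose plus 7 days.
- aPTT is also a safety measure. Dropping triggered samples from the any-value count would hide extreme values at a bleed. This objection is sound, and the fix below respects it.

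**Conclusion.** The gap is real and worth closing before the PD tables are run. Applied literally, SAP 2.1.1 and 2.4 let samples with uncontrolled timing into the FXI and aPTT visit values, the comparisons with placebo, the Day 50 to 176 FXI categories and the aPTT>160s table.

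The effect on group means is likely small: under the assumed values, 0.5 to 1.8 s for aPTT and 0.001 to 0.006 U/mL for FXI per affected subject in the affected window. That is minor beside the roughly 80% FXI reduction the protocol expects. The outputs at risk are the aPTT>160s count, at about 2 percentage points per subject, and the FXI category of subjects close to a boundary. The 0.2 boundary matters because the protocol expects FXI activity to fall to that level or below.

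A stronger reading, that FXI suppression is materially understated or that the dose comparisons are compromised, does not follow. A subject at 0.17 U/mL would need three post-replacement values of 0.35 to change category. These sizes rest on assumed aPTT and FXI values, an assumed bleed frequency, and triggered results reaching the PD dataset.

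**What to change.** 1. In SAP 2.4, base the FXI activity, FXI antigen and aPTT summaries, the comparisons with placebo and the Day 50 to 176 FXI average on scheduled pre-dialysis samples. Use the pre-dialysis wording already applied to the FXI-by-clotting summaries.
2. Keep the any-value aPTT>160s count as a safety display, but show scheduled pre-dialysis samples and triggered samples separately.
3. List triggered and post-transplant values separately, with time since dialysis and since replacement where known.
4. Flag scheduled values that follow logged plasma or factor concentrate, and add a sensitivity summary without them. This is preferable to a fixed exclusion period, whose length would be open to argument.
5. Reconcile the bleed work-up lists in protocol 6.2.2 and 8.5.3, which differ on FXI.

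The cost is SAP wording and a sample-type flag. Transfusions are already logged and concomitant medications coded (SAP 2.3.8). A few values would leave the main PD summaries but stay in the listings. Time relative to dialysis may not be recorded for every triggered sample; where it is missing, the listing should say so.
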